• The HHP will configure the CLARITY® account and remind the family nurse of the process of data upload on the CLARITY® platform. The family nurse will also be reminded to check that the patient fills in the patient diary and to report any adverse event or device deficiencies/failure to the HHP.

| The HHP | will | complete | the | e-CRF |
|---------|------|----------|-----|-------|
|---------|------|----------|-----|-------|

VI.5.3 - ROLES OF THE FAMILY NURSE

For patients of the investigational group:

On Day 3, the family nurse will be trained by the HHP to the upload of data and to data visualisation on the t:connect® platform.

Specific vigilance during the first 7 to 10 days

[figure not shown]
From the first day after patient discharge (Day 3) to the day of first CGM sensor change, the family nurse will visit the patient at least twice a day at 6 hours minimum interval to ensure the patient uses the pump safely, to upload data from the pump to the t:connect® platform, to ensure the patient enters the fixed bolus corresponding to 10% to 20% of his(her) total insulin daily dose as the meal value in the Pump as instructed by the investigator, and to ensure more globally the patient uses the automated insulin delivery system in a right way.

- From 11th day onwards (after the first CGM sensor change), the family nurse will visit the patient every 3 days.
 - At each visit, the family nurse will:
 - change the Pump catheter and refill the cartridge,
 - control the charge of the battery and charge it if necessary,
 - ensure that the patient enters meal value in the pump,
 - ensure that adverse events and device deficiencies/failure are reported by the patient in his/her diary. Any adverse event and/or device deficiencies/failure must be reported by the family nurse to the HHP. Every 3 visits, the family nurse will change the CGM sensor.
 - o upload data from the Pump to the t:connect® visualisation platform.
- For patients of the control group:
 - The frequency of visit(s) at the patient's home will remain the same as before study initiation, as defined by the medical prescription. In addition to usual diabetes care, the family nurse will ensure that adverse events and device deficiencies are reported by the patient in his/her diary.

The family nurse will immediately inform the investigator of any adverse event occurring during the trial.

- Visit 8 at the patient's home will be planned with the HHP.
- Twenty days before the study end (D70, visit 8), a new Dexcom G6 CGM system provided by the HHP will be installed for a 20-day continuous glycaemia recording period. During Visit 8, in addition to usual care, the family nurse will:
 - o Install the new blinded Dexcom G6 CGM system,
 - Be trained by the HHP to the procedure of data upload and data visualisation on the CLARITY® platform,
 - o Be reminded by the HHP on the precautions to use the Dexcom G6 CGM system and on the procedures in case of emergency or technical issues.

VI.6 - END OF STUDY VISIT (V9)

The end of study visit will be performed at the hospital to unequip and remove the devices, and perform the evaluations required by the protocol. All patient materials will be collected and the patient will be switched back to MDI T2D care as per investigator's prescription.

VI.6.1 - ROLES OF THE INVESTIGATOR

At the end of study visit, the Investigator will:

- Remove the Dexcom G6 CGM (for every patient) and the Tandem t:slim X2 Insulin Pump (for patients
 of the investigational group only). Before removing the devices, the Investigator will ensure that data
 have been collected by the HHP.
- Perform the following evaluations:
 - Adverse events and device deficiencies/failure.
 - Concomitant medications.
 - Physical examination, blood pressure and body weight.
 - Laboratory data: HbA1c, blood glucose, total cholesterol, triglycerides, HDL-Cholesterol, LDL-Cholesterol, serum albumin, AST, ALT, gamma GT and serum Creatinine, blood counts (Red Blood Cells (RBC), White Blood Cells (WBC), platelets, haemoglobin, hematocrit) with their sampling date, fasting status, unit and normal range in use.

| - | Collect | , the patient diary and study documentation. |
|---|---------|--|
| | | |
| | | |
| | | |

VI.6.2 - ROLES OF THE HOME HEALTHCARE PROVIDER (HHP)

The HHP will attend the end of study visit at the hospital to:

- Upload data from the Dexcom G6 receiver to the CLARITY® platform for patients of the control group, and data from the Tandem t:slim X2 Insulin Pump to the t:connect® platform for patients of the investigational group,
- Collect and return Dexcom G6 CGM, Tandem t:slim X2 Insulin Pump devices and dedicated laptop (as detailed in section V.4).

VI.6.3 - ROLES OF THE FAMILY NURSE

The family nurse will not attend the end of study visit at the hospital. The HHP will contact the family nurse to provide her (him) with information regarding the new patient MDI T2D care as per investigator's prescription.

VI.7 - ASSESSMENTS AND PROCEDURES

VI.7.1 - PATIENT'S ASSESSMENTS AND PROCEDURES

Figure 2: STUDY FLOWCHART of EXAMINATIONS and EVALUATIONS Figure 2A-Investigational Group

| | SELECTION | INITIATION | RUN-IN | | | FOLL | OW-UP | | |
|---|-----------|-------------|---------------|---------------------|----------------------|------------|------------|------------|------------|
| EXAMINATIONS AND EVALUATIONS | VISIT | VIBIT 1 | VISIT 2 | VISIT 3 | VISIT 4 | VISIT 5 | VISIT 6 | VISIT 7 | VISIT 9 |
| | | | D0-D2 | D3 | D9 | D15 | D30 | D60 | D90 |
| Information letter + Informed consent form | Х | | | | | | | | |
| Demographics child-bearing potential (blood pregnancy test) | X | | | | | | | | |
| Medical and surgical history | X | | | | | | | | |
| Physical examination, blood pressure and body weight (and height at Selection) | Х | X | Х | | | | | | Х |
| Cognitive assessment MOCA and/or MMSE | X | | | | | | | | |
| Concomitant medication | X | Х | Х | X | X | Х | Х | Х | Х |
| Fundus examination | X | | | | | | | | |
| Selection, Inclusion and Non Inclusion criteria | X | Х | | | | | | | |
| Randomisation | Х | | | | | | | | |
| Laboratory data: HbA1c, blood glucose, total cholesterol, triglycerides, HDL-C, | v | | | | | | | | |
| LDL-C, serum albumin, creatinine, AST, ALT, blood counts, gamma GT | X | Х | | | | | | | Х |
| CGM system | | | | 0 | | | | | |
| Patient equipment & training | | X | | | | | | | |
| CGM replacement by family nurse | Х | Х | | Х | Х | Х | Х | Х | |
| CGM removal | | | | | | | | | Х |
| Remote monitoring | Х | Х | | | | | | | |
| Pump System | | | | | | | | | |
| Patient equipment & training | | X Open mode | X Closed-loop | | | | | | |
| Catheter changes & cartridge fill in, battery charge | | Х | X | X | X | X | Х | Х | X |
| Remote monitoring | | | | Х | Х | | Х | Х | Х |
| Pump system removal | | | | | | | | | Х |
| Home Healthcare Provider Services | | | | | 10 10 | | | | |
| Patient 24/7 technical support and motivation | Х | Х | Х | Х | Х | Х | Х | Х | Х |
| Family nurse training | Х | Х | | Х | | | | | |
| Patients, Caregivers training and motivation | Х | Х | Х | Х | | | | | |
| Pump data upload and follow-up | | | Х | X byfamily nurse | X by family nurse | | х | Х | Х |

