The caregiver has to be an adult person, with no known medical condition that in the judgment of the investigator might interfere with the completion of the protocol and who committed to maintaining uninterrupted availability via personal cell phone and to provide assistance to patient. The caregiver must have demonstrated the ability to use basic technology such as a cell phone and to use the automated insulin delivery system as per Home Healthcare Provider (HHP) judgment.

IV.3 - STUDY DURATION FOR THE PATIENT

Trial termination is defined by the date of the last completed visit (actual or planned to be performed at the time of premature withdrawal if applicable) by the last participating patient. The maximum patient's individual study duration will be of 20 weeks.

IV.4 - PREMATURE STUDY DISCONTINUATION

The study could be interrupted temporarily or definitively by the Sponsor and/or the Ethics Committee (EC) and/or the Competent Authority (CA). If such a situation occurs, the investigator should promptly inform the patients and complete the study electronic Case Report Form (e-CRF) with all available data at that time. Study temporary or definitive discontinuation must be declared to Competent Authority (and EC if applicable) in accordance with French local requirements, including its reason such as:

- The investigational intervention is considered as too noxious (as per Ethics Committee (EC) and/or Competent Authority (CA) and/or DSMB (detailed in section IX.3) and/or Sponsor

- A new fact occurs that modifies Sponsor/Competent Authority approval on the trial, such as benefit/risk ratio for instance;
- Any unethical reason;
- Sponsor decision to discontinue the IMD development.

Pharmacovigilance Department recommendation);

Also, patients have the right to withdraw from the study at any time for any reason, without prejudice to further treatment. All the data collected until then will be kept in the study, but not the data collected afterwards.

In addition, the Sponsor or the Investigator may decide to stop the trial or part of the trial at any time for a given patient.

Reasons for individual premature withdrawal recorded by the investigator in the e-CRF will include:

- At least 1 selection or inclusion criterion not met,

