- Any lack of compliance to the study procedures which can compromise the safety of the patient and/or study progress and, in particular, for the investigational group only, the lack of safe and competent use of the automated insulin delivery system in both open and closed-loop features.
- Discontinuation of one of the investigational medical devices during the initiation and/or run-in periods.
- Less than 70% of CGM data recorded during selection period after having retried for an additional 14 days period of CGM recordings.
- Patient's inability to attend study visits, Patient's consent withdrawal, Death.

In these above mentioned cases, the patient will be withdrawn and replaced by another patient who will undergo the study protocol in the same study group if the withdrawal occurs before D3. The "end of study" module of the e-CRF (detailed in section VI.6) will be completed accordingly by the investigator and the date and reason of premature withdrawal will be reported in both the e-CRF and the patient's medical file. These withdrawn patients will return to their usual care therapy i.e., multiple daily injection insulin therapy and nursing care.

V - INVESTIGATIONAL THERAPEUTIC STRATEGY

The study investigational therapy is composed of an automated insulin delivery system made up 2 medical devices and of a tailored home healthcare provider service.

V.1 - Overview of IMD: AN AUTOMATED INSULIN DELIVERY SYSTEM

An automated insulin delivery system uses an automated insulin delivery pump with an automated insulin delivery algorithm and an integrated CGM (iCGM) data to adjust basal insulin delivery and deliver automatic insulin correction boluses. The study automated insulin delivery pump is the Tandem t:slim X2 insulin pump in which the automated insulin delivery algorithm is directly implemented into the pump to form one medical device: the Tandem t:slim X2 insulin pump with the Control-IQ technology. The iCGM data will be transmitted from the Dexcom G6 Continuous Glucose Monitoring (CGM) system. Thus, the study automated insulin delivery system made up of 2 medical devices are:

- The Tandem t:slim X2 Insulin Pump with Control-IQ technology, hereafter entitled the "Pump".

 The Dexcom G6 Continuous Glucose Monitoring (CGM) system (CE marking, class IIb), hereafter entitled the "CGM".

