If a patient withdraws prematurely for any reason after D3, the attributed randomization code and attributed IMD will not be reused nor will the patient be allowed to re-enter in the study afterwards.

V.6 - Intervention duration

Total duration of the intervention will be of approximately 15 weeks from initiation visit (V1) detailed in section VI.3 to end of study visit (V9) detailed in section VI.6 for patients randomised in the study investigational group.

For patients randomised in the control group, the total duration will be approximately 12 weeks from initiation visit (V1) detailed in section VI.3 to end of study visit (V9) detailed in section VI.6.

V.7 - OBSERVANCE/COMPLIANCE

All patients will receive appropriate training in the safe use of the automated insulin delivery system in both open and closed-loop features for investigational group, and training of CGM only for control group.

Patient ability to follow instructions for use of the automated insulin delivery system required by the protocol will be assessed by the investigator during the selection, initiation and run-in periods. The investigator reserves the right to withdraw patients who would not be able to follow the instructions.

Patients will then come back to their initial treatment. These patients will be replaced if the withdrawal occurs before D3.

Observance of patients during the follow-up period will be assessed by patient's family nurse, HHP and investigator, based on the quality of the glycaemic data and information provided by the patient in the patient's diary. Observance data will be collected in the e-CRF.

All patients will have regular contacts with the operational study team during the home study periods including 24/24 hours 7/7 days telephone support by home healthcare providers. In addition, a hotline 24/24h by the investigator center for medical support will be available.

V.8 - CONCOMITANT MEDICATIONS

Any initiation of medication that could interfere with the automated insulin delivery system or with insulin therapy **will not be authorized** during the course of the study. These medications include:

- Glinides,
- Sulfonylurea,
- Glucocorticoids* (*with the exception of patients treated with stable prednisone < at 10 mg equivalent per day since 3 months)
- Or any other medication that could interfere with glycaemic levels.

Authorized glycaemic control concomitant treatments are:

- -Metformin, DDP4 inhibitors, GLP1-receptor agonists.
- -First aid kit

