- For patients randomized to the control group: o The Dexcom G6 sensor will be removed and other parts i.e., receiver and transmitter, collected.
 - The patient will be reminded of the installation of a CGM for 20 days at Day 70.
 The patient will be provided with the schedule of visits at home and at the hospital, with the patient diary
- For patients randomized in the investigational group: Pump will be installed.
 - Patient visit will include 2 nights at hospital for patient observation following the set-up of the Dexcom G6 CGM system with the Pump in open mode.
 - The patient (and the caregiver if applicable) will be trained to the use of the Pump and CGM in open mode, specifically on the management of alarms or alerts on the pump and on meal information entry into the pump for bolus insulin delivery (always the same value to facilitate the entry and avoid carbohydrate calculation). Patients will be provided with a short notice describing the management of meals announcement before leaving hospital.
 - After 48h of observation, the Investigator will ensure that the patient (or the caregiver) is able to go back home and follow the instructions for study continuation, and plan the date of the next visit at the hospital to initiate the

Run-in period. Otherwise, the patient will be withdrawn from the study and replaced.

- The patient will be reminded of the next steps of the protocol and will be provided with the schedule of visits at home and at the hospital, with the patient diary
- The investigator will fill in the e-CRF.
- During the next weeks, the investigator will have access to patient's glycaemic data through the cloud-based t:connect® platform and will be trained by the HHP to the display and exploitation of data on the t:connect® platform. The investigator will receive the report from the HHP following his/her visit at patient home.
- o After Visit 1, the investigator will complete the e-CRF

VI.3.2 - ROLES OF THE HOME HEALTHCARE PROVIDER (HHP)

Patients randomized in the control group:

- The HHP will attend the visit at the hospital to collect the Dexcom G6 CGM devices, the dedicated laptop and fill the related certificate.
- The HHP will contact the family nurse to plan the date for the installation of the Dexcom G6 CGM system at Day 70 at the patient's home.
- The HHP will remind the patient to report adverse events and/or device deficiencies/failure in the patient diary.

Patients randomized in the investigational group:

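### Device-arm patients who fail on the device before D70 are withdrawn after randomisation without D70–D90 CGM, so the primary comparison loses them from one arm only

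*Combined protocol and SAP*

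**What the plan says.** Patients are randomised at the end of selection (V.5, VI.2.1), before any pump is fitted.

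Among the withdrawal reasons in IV.4 are "Discontinuation of one of the investigational medical devices during the initiation and/or run-in periods" and, within the non-compliance item, "for the investigational group only, the lack of safe and competent use of the automated insulin delivery system in both open and closed-loop features". The first is limited to two periods; the second has no period limit. The consequence is the same: "In these above mentioned cases, the patient will be withdrawn and replaced by another patient", with replacement in the same group if this happens before D3. The end-of-study module is completed, and "These withdrawn patients will return to their usual care therapy".

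The visit sections repeat the rule. In VI.3.1, a device-arm patient who cannot go home and follow instructions after the 48-hour observation is handled thus: "Otherwise, the patient will be withdrawn from the study and replaced". VI.4.1 does likewise at run-in, with replacement only before D3. V.7 is permissive: "The investigator reserves the right to withdraw patients who would not be able to follow the instructions".

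No CGM is scheduled after withdrawal. Device-arm follow-up CGM runs through the pump, and Figure 2A has no Visit 8. Controls have a blinded Dexcom G6 fitted at home at D70 for 20 days (VI.5.2, VI.5.3).

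Under X.2.1 the modified ITT set is drawn from the safety set, which requires the patient to be continuing at the end of V1. It also needs at least three adequate CGM days at baseline and again in D70–D90. X.4 interpolates gaps within incomplete days and has no rule for a patient with no D70–D90 TIR at all.

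**The concern.** The primary objective compares a therapeutic strategy with usual care. Being unable to use the device, or stopping it, is one of the outcomes of that strategy. Section I.1.5.2 itself reports that pump discontinuation is more frequent in type 2 than in type 1 diabetes, with most stops before six months linked to acceptability of the device.

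The loss is specific to one arm. A control has the sensor removed at V1, has no run-in and has no pump, so the device-related reasons cannot apply to that patient. The device arm is thereby filtered towards people who can use the system, and is compared with controls who were not filtered in that way. Replacement before D3 restores the numbers in the device arm but strengthens the filter. The per-protocol set is a subset of the modified ITT set, so it cannot reveal the problem. An outcome that was not recorded cannot be recovered by a later choice of analysis set; any all-randomised analysis would have to rest on imputation.

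**Working it through.** **Inputs.** From X.1: difference 17 TIR points, SD 16 in both groups, α 5%, power 90%, 10% allowance for covariate adjustment, 25% non-evaluable. X.3.3 gives the two-sided alternative. The share of the device arm that fails, *f*, is not in the documents. It is assumed here, over 5% to 25%.

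**The plan's own figure.** n = 2 × (16/17)² × (1.960 + 1.282)² = 18.6, so 19; 19 × 1.10 = 20.9, so 21; 21/0.75 = 28 per group, 56 in total. This reproduces X.1, and the other rows of Table 1 reproduce as well.

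**Effect of assignment against effect in completers.** Assume completers gain 17 points and failures, back on usual care, have the control mean. Then:

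- effect of assignment = 17 × (1 − f)
- overstatement when failures are dropped = 17 × f
- device-arm SD with failures included = √(16² + f(1 − f) × 17²)
- power with all 28 per arm observed = Φ(effect/SE − 1.96), where SE = √[(16² + device-arm SD²)/28]. To keep the plan's allowance, 28 is replaced by 28/1.1.

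| f | Effect of assignment | Overstatement | Device-arm SD | Power, 28 per arm | With 10% allowance |
|---|---|---|---|---|---|
| 5% | 16.15 | 0.85 | 16.4 | 96% | 94% |
| 10% | 15.30 | 1.70 | 16.8 | 94% | 91% |
| 15% | 14.45 | 2.55 | 17.1 | 90% | 88% |
| 20% | 13.60 | 3.40 | 17.4 | 86% | 83% |
| 25% | 12.75 | 4.25 | 17.6 | 81% | 77% |

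The last row in full: SD = √(256 + 0.1875 × 289) = 17.6; SE = √(566.2/28) = 4.50; 12.75/4.50 − 1.96 = 0.875; Φ = 0.81. A t-based calculation gives 79.5%, so about 80%.

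**If the strategy has no true effect.** Suppose the failures' D90 TIR would be *d* points below that of device completers. Dropping them shifts the comparison by f × d in favour of the device. With 28 controls observed and SD 16:

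- f = 10% (25 device patients left), d = 8 to 17: shift 0.8 to 1.7 points, two-sided type I error about 5.4% to 6.7%.
- f = 25% (21 left), d = 8 to 17: shift 2.0 to 4.25 points, type I error about 7.2% to 15.1%.

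Both *f* and *d* are assumptions. The direction depends only on failures doing worse than completers.

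**The case against.** Four points can fairly be made in the plan's defence.

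*Scope.* A reader might infer that any stop of the device ends participation, so that D70–D90 CGM is never recorded for any device failure. The documents do not go that far. The discontinuation reason covers only initiation and run-in. A stop during follow-up leads to withdrawal only if it is judged to be non-compliance or unsafe or incompetent use, and V.7 gives the investigator a right, not a duty. VI.7.1.4 names treatment and study discontinuation as distinct things. For a patient who stops in follow-up without being withdrawn, the protocol is silent on how CGM is obtained once the pump is off. A failure several days after D70 may already have the three adequate days needed. This stands, and it limits the point to patients withdrawn before D70, plus that silence.

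*The 25%.* It is tempting to read the allowance in X.1 as a device-failure rate. It covers all causes in both arms, so it can serve only as an upper bound. This stands too.

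*Power.* A reader might expect that retaining these patients raises power. No gain is claimed. Under the same assumptions the current plan, with 21 completers per arm and 17 points, has about 92% power by a t test; the effect of assignment at 25% failure, with all 28 per arm observed, has about 80%. The gain is in what is estimated. The power figures also assume no other missing outcomes, which is optimistic.

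*Data after withdrawal.* IV.4 says "All the data collected until then will be kept in the study, but not the data collected afterwards". That sentence follows the patient's own right to withdraw, so it need not bar follow-up of a patient who only stops the device and still consents.

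The 25% allowance and the replacement rule do not answer the concern: they protect the sample size, not the comparability of the arms.

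**Conclusion.** The concern holds for device-arm patients withdrawn before D70 because they discontinued a device in initiation or run-in, or were judged at any time unable to use the system safely and competently. They were randomised, they will have no D70–D90 CGM, they leave the primary analysis, and no other section repairs this. If failures would do worse than completers, the comparison favours the device.

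The size rests on an assumed failure rate and on failures having control-like TIR: an overstatement of 0.9 points at 5%, 1.7 at 10%, and 4.25 at the 25% upper bound, against an effect of 17 in completers. At the upper bound, power for the effect of assignment is about 80% with everyone observed, or about 77% with the plan's 10% allowance.

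This is an improvement worth making, at low cost. It does not show that the trial would fail, and it says nothing about when a device should be stopped.

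**What to change.** In IV.4, V.7, VI.3.1 and VI.4.1, separate end of device use from withdrawal from the study, leaving the decision to stop a device as it is. Patients who stop the device and still consent stay in follow-up on the care that IV.4 already describes, have the blinded 20-day CGM by the existing Visit 8 procedure, attend V9, and are analysed in the group assigned.

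Three further changes are needed for this to work:

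- **X.2.1:** the efficacy set should not require the patient to be continuing at the end of V1; otherwise patients who stop at V1 remain excluded even with CGM recorded.
- **Replacement before D3:** state that patients who stop the device before D3 are retained and analysed as randomised, even if additional patients are enrolled.
- **D70/D90 anchor:** D0 is the run-in visit in the device arm (Figure 2A) and V1 in controls (Figure 2B), so a device-arm patient who stops before run-in has no D0. Define the planned dates, for example counted from V1 or from the scheduled run-in date.

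The protocol should also say how D70–D90 CGM is obtained for a patient who stops the device in follow-up without leaving the study.

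The cost is a protocol amendment and possible re-consent. Each such patient needs about two sensors, a receiver and transmitter, one home visit, and V9 with its laboratory tests. The staff, devices and CLARITY platform are already in the trial and were used for every patient in selection.

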At the end of the selection period, as detailed in section VI.2.1, study patients will be randomly assigned in a 1:1 ratio to either investigational group or control group according to a central computer-generated randomization scheme upon confirmation of their randomisation by their investigator.

The study randomisation numbers will be allocated sequentially according to a central allocation system, i.e., an Interactive Web Response System (IWRS), to limit the possible study group allocation bias. Before confirming the patient randomization, the investigator should record the patient's birth date (month and year), the informed consent signature date, the gender, the HbA1c level and the confirmation of the inclusion/exclusion criteria met.

The randomization will be performed by block and stratified on the HbA1c level (either <10.0% or ≥10.0%).

The patient will be equipped by the IMD attributed by the IWRS according to his/her randomization number. The randomization number will be automatically registered in the e-CRF at the end of the selection period. The patient will be informed by phone by the Investigator of the allocated group (control/investigational). IMD serial number allocated to each patient will be recorded in the e-CRF at the initiation visit (V1) as per the planned IMD dispensation procedure (see section V.4.4).

The randomization list will be generated via SAS® software by an independent statistician (i.e. out of the study team) of the Clinical Research Organization (CRO) delegated by the Sponsor. One signed paper copy and one electronic copy of the randomization list will be stored at the Quality Assurance Unit of the CRO. The randomization list and individual codes will be kept in the strictest confidentiality until the database lock. They will not be accessible to any study team member before the randomisation of a given patient by his (her) investigator. Especially, the randomisation blocks size(s) will not be revealed to any study team member until the database lock, keeping in mind that this block size may be unique for the whole randomisation list or that a combination of 2 or more variable block sizes may have been introduced in the randomization list prior to its computer-generation.

In case of screening failure prior to patient's randomization, the investigator will specify in the patient's eCRF the date and reason for his (her) non-randomization.

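### Replacing a randomised patient withdrawn before D3 within the same study group lets a known vacancy set the next patient's arm, without a new concealed 1:1 stratified draw

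*Combined protocol and SAP*

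**What the plan says.** **Replacement.** Section IV.4 lists reasons for individual withdrawal and then states that such a patient is "replaced by another patient who will undergo the study protocol in the same study group if the withdrawal occurs before D3". One listed reason arises before randomisation: "Less than 70% of CGM data recorded during selection period after having retried for an additional 14 days period of CGM recordings". Another can arise in one arm only: "for the investigational group only, the lack of safe and competent use of the automated insulin delivery system in both open and closed-loop features". Sections V.7, VI.3.1 and VI.4.1 also provide for replacement. They do not say which group the replacement joins, and VI.3.1 omits the D3 limit.

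**Allocation.** Section V.5 states that "study patients will be randomly assigned in a 1:1 ratio to either investigational group or control group", through sequential IWRS numbers. It adds: "The randomization will be performed by block and stratified on the HbA1c level". On concealment of the list and codes it says: "They will not be accessible to any study team member before the randomisation of a given patient by his (her) investigator". Patients who fail before randomisation are handled separately, by recording "the date and reason for his (her) non-randomization". The only sentence in V.5 on codes after withdrawal is: "If a patient withdraws prematurely for any reason after D3, the attributed randomization code and attributed IMD will not be reused". No step for allocating a replacement is described.

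**Timing and knowledge of the arm.** Under VI.2.1 the investigator randomises at the end of the selection period, before V1, and then phones the result to the patient. Section III describes an open-label trial at approximately 10 hospitals.

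**The concern.** A concealed draw protects the comparison because whoever judges eligibility cannot know which arm the next patient will receive. Under IV.4, once a randomised patient leaves before D3, the arm of the replacement is settled before that person is chosen. An investigator who knows that the vacancy is in the device arm could, even without intending to, look for a candidate more likely to cope with the device.

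The replacement also counts in the primary analysis. A patient withdrawn before D3 has no CGM record from D70 to D90 and so cannot enter the modified ITT efficacy set of X.2.1, whereas the replacement can. With 28 patients planned per arm, a few such entries could matter if they were selected.

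**Working it through.** **1. Does the rule reach randomised patients?** Yes. Randomisation is at the end of selection (V.5, VI.2.1). V1 follows, and D3 comes after V1 in both arms. VI.3.1 provides for replacement after the 48 h stay at V1, and VI.4.1 at the run-in visit. Both apply to patients who already have an arm.

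**2. What sets the replacement's arm?** There are three ways to read the text:

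| Reading | Source of the arm | Known before the next patient is chosen? |
|---|---|---|
| IV.4 as written, no code reused | the vacated arm | yes, at the withdrawing site |
| Freed code reissued (V.5 bars reuse only after D3, so reuse before D3 is implied but not stated) | the list, as drawn for the withdrawn patient | yes, at the withdrawing site |
| V.5 as for any new patient | next stratified 1:1 allocation | no |

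Only the third keeps allocation concealed, and it is not what IV.4 says. The documents do not say whether the replacement must come from the same HbA1c stratum, or whether it must come from the same site.

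**3. Is exposure equal in the two arms?** Figure 2A places D0 to D2 at V2 in the investigational arm. Figure 2B places D0 at V1 in control.
- Investigational arm, V1 to D3: 14 + 3 = 17 days, or 2 + 14 + 3 = 19 days if the 48 h stay is counted separately (VI.3).
- Control, V1 to D3: 3 days. Figure 2B has no D3 visit, so this is D0 plus 3.
- Difference: 17 - 3 = 14 to 19 - 3 = 16 days.
- V.6 gives approximately 15 and 12 weeks from V1 to V9, a difference of 3 weeks, or 21 days. For control, 12 x 7 = 84 days is itself short of 90, so V.6 cannot settle the exact gap.

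The supportable statement is that the window is roughly two to three weeks longer in the investigational arm. The time between randomisation and V1 is also exposed, in both arms. In addition, one IV.4 reason and the capability-based replacements in VI.3.1 and VI.4.1 concern the investigational arm only.

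**4. The plan's own sample size.** X.1 uses a difference of 17, SD 16, 5% type 1 error and 90% power; the test is two-sided (X.3.3).
- n = 2 x 16²/17² x (1.960 + 1.282)² = 18.6 per arm
- 18.6 x 1.10 = 20.5, rounded up to 21
- 21/0.75 = 28 per arm, 56 in total

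The plan's figures reproduce. The allowance for non-evaluable patients is 28 - 21 = 7 per arm.

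**5. What would a fresh draw cost in power?** Assume 3 or 7 losses before D3, all in the investigational arm, and a further 25% lost in both arms. Evaluable patients are 0.75 x n, rounded down. Power is for a two-sided 5% t-test using the noncentral t, with noncentrality 17/(16 x √(1/n₁ + 1/n₂)) and no gain from covariates.

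| Scenario | Entering (inv. / control) | Evaluable | Power |
|---|---|---|---|
| As planned | 28 / 28 | 21 / 21 | 0.919 |
| 3 lost, fresh draws split evenly | 26.5 / 29.5 | 19 / 22 | 0.911 |
| 7 lost, fresh draws split evenly | 24.5 / 31.5 | 18 / 23 | 0.909 |
| 3 lost, all fresh draws in control | 25 / 31 | 18 / 23 | 0.909 |
| 7 lost, all fresh draws in control | 21 / 35 | 15 / 26 | 0.892 |
| 3 lost, no replacement | 25 / 28 | 18 / 21 | 0.896 |
| 7 lost, no replacement | 21 / 28 | 15 / 21 | 0.863 |

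The first column counts patients still in the trial after the early losses and any additions. Same-arm replacement therefore protects little power that a fresh draw would lose.

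**The case against.** The strongest reply is that the IWRS can reissue the freed code. The arm would then come from the computer-generated list, and block balance would be kept. If the next eligible patient took that code whatever their characteristics, allocation would remain unrelated to prognosis. Bias needs both knowledge of the vacancy and selection on it. Knowledge is certain only at the withdrawing site, and nothing says that other sites learn of a vacancy. The primary ANCOVA (X.3.3) also adjusts for baseline TIR and HbA1c category.

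Much of this stands. A reader might infer that IV.4 and V.5 flatly contradict each other. They need not, because V.5 leaves room for code reuse before D3. A reader might also infer that the comparison is biased. The documents do not support that: they give no number of replacements, and nothing on how replacements are chosen. Nor is a total above 56 caused by the same-group rule, since replacing patients by fresh draw raises the number entering in the same way.

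Reuse does not restore concealment, however: the reissued arm is already known to the investigator who phoned it to the withdrawn patient. Covariate adjustment limits the effect of selecting on baseline TIR or HbA1c category, but not on unmeasured traits such as ability to manage the device. Analysis by IWRS-assigned device (X.2.1) does not address how the assignment came about.

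**Conclusion.** The point holds as a gap in allocation and concealment. As written, the arm of a replacement for an already randomised patient is set by a vacancy known at the withdrawing site, and V.5 provides no concealed step to prevent that. Foreseeability rests on the vacancy being filled at that site, which the documents neither require nor exclude.

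The rule probably acts more often in the investigational arm. The direction of the difference in exposure is well supported, but its length is only approximate.

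The number of replacements and the size and direction of any bias cannot be derived and may be zero. The sample-size calculation is unaffected. This is a cheap improvement to the plan, not a demonstrated fault in its result. The power figures depend on the assumed 3 or 7 early losses, all in one arm, with a further 25% loss in both.

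**What to change.** - **IV.4:** separate screening failures before randomisation, which V.5 already covers, from withdrawals after it. Delete the requirement that the replacement join the same group.
- **V.5:** state that no randomisation code is reused at any time after randomisation, and that any additional patient is randomised as a new patient by the next stratified 1:1 IWRS allocation.
- **Consistency:** align V.7, VI.3.1 and VI.4.1, and the wording on 28 patients per group in the synopsis, III and X.1.
- **Reporting:** give withdrawals before D3, and any same-arm replacements already made, by arm. Add one sensitivity analysis of the primary endpoint that excludes those replacements.

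The withdrawal reasons and the D3 cut-off stay as they are.

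The cost is a protocol amendment, which may need authority and ethics committee review under XIII.7, an IWRS change and slightly uneven arms. Recruitment status is not given. If recruitment is finished, only the reporting and the sensitivity analysis apply. Under the assumptions above, power is about 91% at 19 versus 22 or 18 versus 23 evaluable patients and about 89% at 15 versus 26, compared with about 92% at 21 versus 21.
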